13. STUDY MEDICATION COMPLIANCE

Compliance during the regular treatment period will be assessed using relative dose intensity during the regular treatment period.

Compliance during the regular treatment period will be summarized using descriptive statistics, i.e., number of subjects (n), mean, median, standard deviation (SD), 25th and 75th percentiles (Q1, Q3), minimum and maximum.

The compliance will also be summarized by the number of subjects in each of following categories:

- <80%
- 80% to 120% (including the 80% and 120%)
- >120%

The compliance categories will be summarized by count(s) and percentages (%).

Subjects with missing compliance information will be presented in a separate category, if applicable.

14. EFFICACY OUTCOMES

14.1. EFFICACY ASSESSMENT

Complete Mayo Score

Document: Statistical Analysis Plan

Author: [name]

Version Number: 1.1

Version Date: 18Jan2023

Template No.: CS_TP_BS016 Revision 5

Reference: CS_WI_BS005

Effective Date: 01Apr2018

The Mayo score is a standard, widely accepted, digital assessment of UC severity in subjects. The Mayo scores range from 0 to 12 and consist of 4 sub-items, each with the score range from 0 to 3. The higher the score is, the more severe the disease is:

1. Stool frequency ^a

- 0 = Normal numbers of stools for this patient
- 1 = 1-2 stools more than normal
- 2 = 3-4 stools more than normal
- 3 = 5 or more stools than normal

2. Rectal bleeding ^b

- 0 = No blood seen
- 1 = Streaks of blood with stool less than half the time
- 2 = Obvious blood with stool most of the time
- 3 = Blood alone passes

3. Endoscope findings

- 0 = Normal or inactive disease
- 1 = Mild disease (erythema, decreased vascular pattern, mild friability)
- 2 = Moderate disease (marked erythema, lack of vascular pattern, friability, erosions)
- 3 = Severe disease (spontaneous bleeding, ulceration)

4. Physician's global assessment ^c

- 0 = Normal
- 1 = Mild disease
- 2 = Moderate disease
- 3 = Severe disease

Notes:

a. Each patient serves as his or her own control to establish the degree of abnormality of the stool

Document: Statistical Analysis Plan

Author: [name]

Version Number: 1.1

Version Date: 18Jan2023

Template No.: CS_TP_BS016 Revision 5

Reference: CS_WI_BS005

Effective Date: 01Apr2018

frequency.

- b. The daily bleeding score represents the most severe bleeding of the day.
- c. The physician's global assessment acknowledges the 3 other criteria, the patient's daily recollection of abdominal discomfort and general sense of well-being, and other observations, such as physical findings and the patient's performance status.

Complete Mayo scores at baseline and at week 12 are calculated based on the results in the above items 1, 2, 3, and 4 (stool frequency, rectal bleeding, endoscopic findings, and physician's global assessment).

Adapted Mayo score

Adapted Mayo score is calculated based on the above assessment 1, 2 and 3 (Stool frequency, Rectal bleeding and Endoscopic findings). The Adapted Mayo score will be calculated at the visit at screening and week 12 (or early termination visit) during stage 1 study as well as at week 24 (only sub-study 2) and week 48 (or early termination visit) during stage 2 study.

Partial Mayo scores

Partial Mayo scores will be calculated at weeks 2, 4, 8 and 12 (i.e., Mayo score without colonoscopy findings) in study stage 1. In sub-study 1 of study stage 2, partial Mayo scores will be calculated at weeks 18, 24, 32 and 40. In sub-study 2 of study stage 2, partial Mayo scores will be calculated at weeks 16, 32 and 40.

Partial Mayo scores will be calculated based on assessment in the items 1, 2, and 4 of section 14.1.1 (Stool frequency, Rectal bleeding and Physician's global assessment).

14.2. PRIMARY EFFICACY

14.2.1. PRIMARY EFFICACY ENDPOINT

The primary efficacy analysis is based on the primary efficacy endpoint: change in adapted Mayo

Document: Statistical Analysis Plan

Author: [name]

Version Number: 1.1

Version Date: 18Jan2023

Template No.: CS_TP_BS016 Revision 5

Reference: CS_WI_BS005

Effective Date: 01Apr2018

score from baseline at week 12 compared between CBP-307 0.2 mg and placebo.

14.2.2. PRIMARY ANALYSIS OF PRIMARY EFFICACY ENDPOINT

The primary efficacy analysis will be based on FAS, mFAS, and PPS.

The covariance (ANCOVA) model with baseline as covariate will be used to analyze the changes in adapted Mayo score from baseline at week 12 between the CBP-307 0.2 mg group and the placebo group stratified by whether the previous treatment with a tumor necrosis factor (TNF)- α antagonist failed (Yes or No). The superiority of the CBP-307 0.2 mg group to placebo on change in adapted Mayo score from baseline at week 12 after treatment will be tested at a significance level of 0.025 with one-sided. If the significance level is reached, then superiority of the CBP-307 0.2 mg will be statistically significant. For subjects enrolled in protocol version 5.0 or earlier in 0.1 mg group, they will be compared with placebo group with same method as 0.2mg QD group, but only results of 0.1 mg group will be presented as supportive results.

The least square mean (LSMEANS), together with the p values and the 95% confidence intervals, between 0.2 mg vs. placebo will be reported using the ANCOVA model (SAS PROC MIXED), with the stratification factor as the confounding factor in the ANCOVA model and the baseline values as covariate.

The change from baseline over time on the Adapted Mayo score will also be plotted by each treatment group for exploratory purpose.

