4 STUDY OBJECTIVES AND ENDPOINTS

	Study objectives	Study endpoints				
Primary	To compare clinical efficacy of CBP-307 vs placebo by evaluating the change of adapted Mayo score after 12 consecutive weeks treatment in subjects with moderate to severe UC	Change in adapted Mayo score from baseline at week 12 compared between CBP-307 0.2 mg and placebo				
Secondary	To compare clinical efficacy of CBP-307 vs placebo by evaluating the clinical response rate, clinical remission rate and mucosal healing rate after 12 consecutive weeks treatment in subjects with moderate to severe UC	 Change in adapted Mayo score from baseline at week 12 compared between CBP-307 0.1 mg and placebo Change in complete Mayo score from baseline at week 12 after treatment Comparison of clinical response rate at week 12 by adapted Mayo score (defined as a decrease of ≥ 2 points and at least 30% from baseline, accompanied with a decrease of ≥ 1 point from baseline in the rectal bleeding subscore or an absolute rectal bleeding subscore of ≤ 1 point) Comparison of clinical response rate at week 12 by complete Mayo score (defined as a decrease of ≥ 3 points and at least 30% from baseline, 				

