6. GENERAL CONSIDERATIONS

Analysis results will be presented using descriptive statistics. For categorical variables, the number and percentage of subjects in each category will be presented; for continuous variables, the number of subjects [n], mean, standard deviation [SD] or standard error [SE], median, minimum, and maximum will be presented. Statistical comparisons will be tested at two-sided alpha of 0.05 significance level, unless otherwise specified. Data collected in the study will be presented in by-subject listings for all subjects in the full analysis set (efficacy analysis) and safety analysis set

Document: Statistical Analysis Plan

Author: [name]

Version Number: 1.1

Version Date: 18Jan2023

Template No.: CS_TP_BS016 Revision 5

Reference: CS_WI_BS005

Effective Date: 01Apr2018

(safety analysis), unless otherwise specified. All by subject listings will be presented by treatment group, subject identification number in ascending order, unless otherwise specified.

For stage 1 analysis, the analysis period for subjects who enroll stage 2 will be from screening (baseline visit) in stage 1 until before the first dose of stage 2. And for subjects who will not enroll stage 2 (including screen failed subjects before randomization, randomized subjects but not treated, and subjects early discontinued in stage 1), the analysis period will be from screening (baseline visit) in stage 1 until end of study in stage 1. For stage 2 sub-study 1 analysis, the full/safety analysis population will be the randomized subjects who receive at least one dose of study medication or placebo in stage 2, but the analysis period will be from screening (baseline visit) in stage 1 until the end of study in stage 2. But for subjects who will enroll stage 2 sub-study 2, the analysis period will be the date of first dose of the open-label CBP307 0.2mg in stage 2 until the end of study in stage 2 since treatment is changed to open-label CBP307 0.2 mg QD.

For 0.2mg (all stages) group, the analysis period will be the date of first dose of initial administration until the end of stage 2 study, including stage 2 sub-study 1 and stage 2 sub-stage 2.

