7.4. SAMPLE SIZE

Approximately 134 subjects with moderate to severe UC will be randomized in the study. Among them, there are approximately 30 subjects in the CBP-307 0.1 mg once daily group. In protocol version 5.0 or earlier, 195 patients with moderate to severe UC were planned to be randomized at 1:1:1 into any of the following 3 groups: CBP-307 0.1 mg once daily, CBP-307 0.2 mg once daily, placebo. Approximately 65 subjects were planned to be in each group. However, protocol amendment happens during the treatment period. The primary endpoint analysis is based on the comparison between the 0.2 mg CBP-307 group and the placebo group, and protocol version 6.0 keeps only these two groups, and sample size is re-calculated. The 0.1 mg group is not applicable in protocol version 6.0, and there will be no further subjects enrolled in the 0.1 mg group. The nearly 30 subjects already randomized with protocol version 5.0 or earlier are kept and analyzed for exploratory purpose.

The sample size re-calculation is based on the comparison between CBP-307 0.2 mg once daily group and placebo group on the primary efficacy endpoint, namely the change in adapted Mayo score from baseline at week 12 after treatment. Assuming that the difference between the 0.2 mg group and the placebo group of the change from baseline at week 12 after treatment in adapted Mayo score is 1.2, and the common standard deviation is 2.0, a significance level of $\alpha=0.05$ (two-sided), and a dropout rate is 15%, then each group needs to enroll at least 52 subjects (104 subjects in two groups) to provide a power of 80% to detect the difference between the 0.2 mg group and the placebo group on the primary efficacy endpoint. Based on this estimation, the eligible subjects with moderate to severe UC will be randomized at 1:1 into CBP-307 0.2 mg once daily group or placebo group until 52 subjects are enrolled into each group.

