14.3.1. SECONDARY ANALYSES ON EFFICACY ENDPOINTS

- Change in adapted Mayo score at week 12 from baseline: 0.1 mg vs placebo (only 0.1 mg group presented)
- Change in complete Mayo score at week 12 from baseline: 0.2 mg vs placebo
- Change in complete Mayo score at week 12 from baseline: 0.1 mg vs placebo (only 0.1 mg group presented)
- Clinical response rate by Adapted Mayo Score at week 12: 0.2 mg vs placebo (defined as a decrease of ≥ 2 points and at least 30% from baseline, accompanied with a decrease of ≥ 1 point from baseline in the rectal bleeding subscore or an absolute rectal bleeding

Document: Statistical Analysis Plan

Author: [name]

Version Number: 1.1

Version Date: 18Jan2023

Template No.: CS_TP_BS016 Revision 5

Reference: CS_WI_BS005

Effective Date: 01Apr2018

subscore of <= 1 point)

- Clinical response rate by Adapted Mayo Score at week 12: 0.1 mg vs placebo
- Clinical response rate by Complete Mayo Score at week 12: 0.2 mg vs placebo (defined as a decrease of >= 3 points and at least 30% from baseline, accompanied with a decrease of >= 1 point from baseline in the rectal bleeding subscore or an absolute rectal bleeding subscore of <= 1 point)
- Clinical response rate by Complete Mayo Score at week 12: 0.1 mg vs placebo
- Clinical remission rate by Adapted Mayo score at week 12: 0.2 mg vs placebo (defined as a rectal bleeding subscore = 0 and stool frequency sub score <= 1, with an Endoscopy subscore <=1 [excluding friability])
- Clinical remission rate by Adapted Mayo score at week 12: 0.1 mg vs placebo
- Clinical remission rate by Complete Mayo score at week 12: 0.2 mg vs placebo (defined as a total Mayo score of <= 2 points with no individual subscore > 1 point)
- Clinical remission rate by Complete Mayo score at week 12: 0.1 mg vs placebo
- Mucosal healing rate at week 12: 0.2 mg vs placebo (defined as Mayo endoscopic subscore <= 1)
- Mucosal healing rate at week 12: 0.1 mg vs placebo

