14.3.3. ANALYSIS OF SECONDARY EFFICACY VARIABLES

Unless otherwise specified, all secondary efficacy analyses will be performed between treatment group and placebo and based on FAS and PPS. All results of these comparative analyses are used for exploratory purpose.

The clinical response rate at week 12, clinical remission rate at week 12, and mucosal healing rate at week 12 will be analysed

Summary statistics of qualitative statistic will be provided by each treatment group. Statistical comparison between the 0.2 mg CBP-307 group versus the placebo group and between 0.1 mg versus placebo group will be conducted using the Cochran Mantel Haenszel (CMH) test, stratified by whether treatment with a tumor necrosis factor (TNF)- α antagonist failed (Yes or No). The p-value on the rate difference and the 95% Newcombe confidence interval (CI) will be provided.

For example:

The null hypothesis to be tested is that the clinical response rate at week 12 is not different between the 0.2 mg treatment group and the placebo treatment group; i.e.,

$$H_0: \text{clinical response rate at week 12}_{0.2 \text{ mg}} = \text{clinical response rate at week 12}_{\text{placebo}}$$

The alternative hypothesis is that clinical response rate at week 12 in the 0.2 mg treatment group is higher than that of the placebo treatment group, i.e.,

$$H_A: \text{clinical response rate at week 12}_{0.2 \text{ mg}} \neq \text{clinical response rate at week 12}_{\text{placebo}}$$

Document: Statistical Analysis Plan

Author: [name]

Version Number: 1.1

Version Date: 18Jan2023

Template No.: CS_TP_BS016 Revision 5

Reference: CS_WI_BS005

Effective Date: 01Apr2018

for quantitative summary statistics, the least square mean (LSMEANS), together with the p values and the 95% confidence intervals, between 0.2 mg vs. placebo and between 0.1 mg vs. placebo will be reported using the ANCOVA model (SAS PROC MIXED), with the stratification factor as the confounding factor in the ANCOVA model and the baseline values as covariate.

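### Minor: the exploratory 0.1 mg comparisons use an unrestricted placebo group, an estimated 42% of it randomised after the 0.1 mg arm closed, with no concurrent-only check

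*SAP*

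**What the plan says.** **How the arms were filled.** SAP 7.4 (and Protocol 9.2) says that under version 5.0 or earlier "195 patients with moderate to severe UC were planned to be randomized at 1:1:1" to 0.1 mg, 0.2 mg and placebo. From version 6.0 "there will be no further subjects enrolled in the 0.1 mg group", which stands at about 30. Randomisation then continues 1:1 to 0.2 mg or placebo "until 52 subjects are enrolled into each group". The overall total is about 134.

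**What is compared.** Protocol 4 lists week 12 change in adapted Mayo score "compared between CBP-307 0.1 mg and placebo" as a secondary endpoint. SAP 14.2.2 has the 0.1 mg subjects "compared with placebo group with same method as 0.2mg QD group, but only results of 0.1 mg group will be presented as supportive results". SAP 14.3.1 repeats it: "Change in adapted Mayo score at week 12 from baseline: 0.1 mg vs placebo (only 0.1 mg group presented"). It adds 0.1 mg contrasts for complete Mayo change, two response rates, two remission rates and mucosal healing. SAP 14.3.3 says the comparison "between 0.1 mg versus placebo group will be conducted using the Cochran Mantel Haenszel (CMH) test", stratified by prior anti-TNF failure. SAP 14.4.2 carries the comparison to IBDQ and to stage 2 sub-study 1, and Appendix 2 tabulates the stage 1 versions.

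**What is adjusted for.** The Mayo-score ANCOVA has baseline and the anti-TNF stratum. The CMH test has the anti-TNF stratum only. None of the analysis sets in SAP 5.1 to 5.3 is defined by protocol version, and SAP 7.3 plans no subgroup analyses.

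**Status.** SAP 14.2.2 calls the 0.1 mg results supportive. Protocol 9.8.2.2 and SAP 14.3.3 call all secondary comparisons exploratory, and Protocol 9.13 says the same of everything outside the primary analysis.

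**The concern.** A 0.1 mg subject could only have been randomised while that arm was open. A placebo subject randomised under version 6.0 never had a chance of receiving 0.1 mg. Randomisation therefore protects only the part of the 0.1 mg contrast that uses concurrent placebo subjects. If placebo outcomes moved between the two periods for reasons that baseline score and anti-TNF status do not capture, the move is read as a 0.1 mg effect, in either direction.

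Some change over time is plausible. Protocol 1 plans the study from March 2018 to September 2022, SAP 1 dates version 6.0 to 25 December 2020, and SAP 3.3 adds the mFAS because COVID-19 disturbed week 12 assessments. None of this measures a shift.

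What is at stake is how the 0.1 mg estimates, p-values and intervals can be read. As written, the plan offers no 0.1 mg contrast that is fully randomised. Because the change-score outputs are to show only the 0.1 mg group, a reader may not see which placebo subjects it was compared with.

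**Working it through.** **1. The plan's own sample size.** Inputs from SAP 7.4: difference 1.2, SD 2.0, two-sided 0.05, power 80%, dropout 15%. n = 2 x (1.96 + 0.842)^2 x 2.0^2 / 1.2^2 = 43.6, so 44 per group; 44 / 0.85 = 51.8, so 52. This reproduces the stated figure.

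**2. Do the 52 placebo subjects span both versions?** 134 - 30 = 104 = 2 x 52, so yes. If all 104 were new under version 6.0, on top of about 3 x 30 = 90 earlier subjects, the total would be about 194, which contradicts 134.

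**3. Non-concurrent share.** With c concurrent placebo subjects the share is (52 - c)/52. The documents give no c. Even 1:1:1 allocation with 30 on 0.1 mg implies c of about 30; 36 and 24 are illustrative bounds.

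- c = 36: 16/52 = 31%
- c = 30: 22/52 = 42%
- c = 24: 28/52 = 54%

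**4. Bias.** If later placebo subjects differ by D after adjustment, the pooled placebo mean moves by 0.423 x D. Assumed D of 0.25 and 0.5 points gives 0.11 and 0.21 points.

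**5. Precision (SD 2.0, no dropout, c = 30).**

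- Pooled: 2 x sqrt(1/30 + 1/52) = 0.459.
- Concurrent-only: 2 x sqrt(1/30 + 1/30) = 0.516, ratio 1.126. At c = 36 and c = 24 the SE is 0.494 and 0.548, so 8% and 19% wider.
- Three arms with a version term, cells 30/30/30 then 0/22/22: the placebo mean under version 5.0 has a direct estimate with variance 4/30 = 0.133 and an indirect one through 0.2 mg with variance 4/30 + 4/22 + 4/22 = 0.497. Combined: 1/(1/0.133 + 1/0.497) = 0.105. Adding 0.133 for the 0.1 mg mean gives SE = sqrt(0.238) = 0.488, ratio 1.065.

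**6. Bias against variance.** Pooled RMSE = sqrt(0.459^2 + (0.423 x D)^2): 0.471 at D = 0.25 and 0.505 at D = 0.5. Pooling stops being the better choice at |D| = sqrt(SE_alt^2 - 0.459^2)/0.423, which is 0.40 for the three-arm model and 0.56 for concurrent-only.

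**7. Error rate.** SAP 6 sets the general rule: "Statistical comparisons will be tested at two-sided alpha of 0.05 significance level, unless otherwise specified". P(|Z + 0.423 x D/0.459| > 1.96) is 5.6% at D = 0.25 and 7.5% at D = 0.5, against 5%.

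**8. Illustrative power at 1.2 points.** SAP 3.3 anticipates about 20% missing at week 12, so each SE is divided by sqrt(0.8): 0.513, 0.546 and 0.577. Power is about 65% pooled, 59% three-arm and 55% concurrent-only. The 1.2 is the difference assumed for 0.2 mg; no 0.1 mg effect is assumed anywhere.

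**The case against.** The strongest reply is that little rests on these results. They carry no alpha, are labelled supportive or exploratory throughout, and Protocol 5.2.2 already gives the sponsor's reasons for continuing with 0.2 mg alone. That stands, and it caps the point at minor.

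A second reply is that pooling is a legitimate choice. By step 6 it has the lower mean squared error until |D| passes about 0.40 (three-arm) or 0.56 (concurrent-only), and no D is documented. That also stands. A reader might infer that the main 0.1 mg analysis should be replaced by a three-arm or concurrent-only one, but the documents do not support this. It would be a bias-variance preference, and the three-arm model would in any case serve only change scores, while five of the seven 0.1 mg endpoints in SAP 14.3.1 are rates.

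Third, SAP 14.2.2 never says that all placebo subjects are used. It names the placebo group without restriction and no concurrent set is defined, so unrestricted is the plain reading, but it is a reading.

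None of these replies removes the gap: a mixed control group with no planned check and no planned disclosure of its composition.

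**Conclusion.** The point holds as a minor, inexpensive improvement. The 0.1 mg contrasts draw on an unrestricted placebo group, of which about 42% would be non-concurrent (31% to 54% over the range shown). This rests on even 1:1:1 allocation having given about 30 concurrent placebo subjects; it is inferred, not stated. The possible bias is about 0.42 x D, with D unknown.

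Two stronger readings are not supported. A reader might infer that the 0.1 mg results are biased; the documents give no drift figure, so bias is possible, not shown. A reader might also infer that the primary result is affected. It is not: 0.2 mg and placebo were allocated equally to each other under both versions, so that comparison is concurrent throughout.

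**What to change.** 1. Keep the planned analysis as the main 0.1 mg estimate.
2. Add a sensitivity analysis for the stage 1 change scores (including IBDQ) and rates, using only placebo subjects randomised under version 5.0 or earlier. Compute both the CMH test and the Newcombe interval on that restricted set. Adding version as a CMH stratum would handle the p-value, because version 6.0 strata hold no 0.1 mg subjects, but SAP 14.3.3 does not say the Newcombe interval is stratified.
3. Classify subjects by protocol version at randomisation, not by a calendar date, because Protocol 2.1 lets an amendment take effect only after ethics approval.
4. Report placebo N by version next to each 0.1 mg result.
5. State non-concurrency as a limitation, including for sub-study 1. Entry there depends on week 12 response, so restricting the comparator would not restore randomisation.
6. Optionally, for change scores, add a three-arm ANCOVA with a version term as a further sensitivity analysis. It assumes the same version shift in 0.2 mg and placebo. If it is used, version should also enter the multiple imputation model, since the inputs listed in SAP 14.2.3 omit it.

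The cost is SAP wording, one derived variable and a few supplementary outputs. The concurrent-only interval is about 13% wider (SE 0.516 against 0.459). The primary analysis does not change.

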14.2.3. MISSING IMPUTATION FOR PRIMARY EFFICACY

Multiple Imputation

Multiple imputation has 3 distinct phases: Imputation, Analysis and Combining. During the Imputation Phase, the missing data values are filled-in to form a complete dataset. This is done 'm' times. For the Analysis Phase, each of the 'm' complete datasets are analysed by a statistical

Document: Statistical Analysis Plan

Author: [name]

Version Number: 1.1

Version Date: 18Jan2023

Template No.: CS_TP_BS016 Revision 5

Reference: CS_WI_BS005

Effective Date: 01Apr2018

model (as specified in Section 14.2.2). The Combining Phase pools the parameter estimates with their standard errors across the ‘m’ complete datasets and produces an average estimate with a standard error calculated using Rubin’s formula this allows for the uncertainty between imputations as well as the variability within each analysis.

Multiple imputation assumes that the data are missing at random (MAR). MAR assumes that the missingness does not depend on the actual missing values, but that the missing data can be completely explained by the observed data. To test the robustness of the multiple imputation strategy a tipping point analysis may be implemented.

In the case of mayo scores, a multiple imputation approach is implemented for the missing individual adapted mayo score.

Each individual mayo score is imputed and then the composite endpoint measures are created (see list of endpoints in APPENDIX 2).

There are 4 steps to this process:

1. Create a dataset with one record per subject, containing all values of each mayo score for all visits (baseline and week 12 on one record) in stage 1. These variables are included because they are correlated with the endpoint and/or missingness. The multiple imputation process creates complete datasets using PROC MI in SAS 9.4. During post-processing, the endpoints are derived in each of the complete datasets. The endpoints and analysis model in APPENDIX 2.
2. Run ‘m’ times Markov Chain Monte Carlo (MCMC) imputations to make the missing values in the dataset have a full missingness pattern. This will produce a dataset with an index variable _imputation_ and otherwise the same variables as the input dataset. It will have one record per imputation per subject.
3. Run analysis of covariance model (the method in section 14.2.2) with imputation on each imputed dataset from Step 2. This will generate a dataset with the same structure as the input dataset, but will have the missing values filled in.
4. Combine all estimated statistics into one using PROC MIANALYZE.

Document: Statistical Analysis Plan

Author: [name]

Version Number: 1.1

Version Date: 18Jan2023

Template No.: CS_TP_BS016 Revision 5

Reference: CS_WI_BS005

Effective Date: 01Apr2018

